### **7.6.2      Serious Adverse Events**

Serious adverse events will be summarized :

- Overall summary of SAEs by worst CTC grade (any grade, grade 3-4, grade 5) presented by SOC/PT.
- Overall summary of drug-related SAEs by worst CTC grade (any grade, grade 3-4, grade 5) presented by SOC/PT.

A by-subject SAE listing will be provided for the “enrolled subjects” population.

### **7.6.3      Adverse Events Leading to Discontinuation of Study Therapy**

AEs leading to discontinuation will be summarized:

- Overall summary of AEs leading to discontinuation by worst CTC grade (any grade, grade 3-4, grade 5) presented by SOC/PT.
- Overall summary of drug-related AEs leading to discontinuation by worst CTC grade (any grade, grade 3-4, grade 5) presented by SOC/PT.

A by-subject AEs leading to discontinuation listing will be provided.

### **7.6.4      Adverse Events Leading to Dose Modification**

AEs leading to dose delay/reduction will be summarized:

- Overall summary of AEs leading to dose delay/reduction by worst CTC grade (any grade, grade 3-4, grade 5) presented by SOC/PT.
- Overall summary of related AEs leading to dose delay/reduction by worst CTC grade (any grade, grade 3-4, grade 5) presented by SOC/PT.

A by-subject AEs leading to dose delay/reduction listing will be provided.

### **7.6.5      Adverse Events**

Adverse events will be summarized:

- Overall summary of any AEs by worst CTC grade (1, 2, 3, 4, 5, not reported, total) presented by SOC/PT.

- Overall summary of any AEs that required immune modulating medication by worst CTC grade (any grade, grade 3-4, grade 5) presented by SOC/PT.
- Overall summary of drug-related AEs by worst CTC grade (1, 2, 3, 4, 5, not reported, total) presented by SOC/PT.
- Overall summary of drug-related AEs by worst CTC grade (any grade, grade 3-4, grade 5) presented by SOC/PT.

A by-subject AE listing will be provided. A by-subject listing of any AE requiring immune modulating medications will also be provided.

### **7.6.6     Select Adverse Events (EU/ROW Submissions)**

Unless otherwise specified, analyses will be performed by select AE category. Analyses will also be repeated by subcategory of endocrine events.

#### **7.6.6.1    Incidence of Select AE**

[figure not shown]
Select AEs will be summarized for each category/subcategory:

- Overall summaries of any select AEs by worst CTC grade (any grade, grade 3-4, grade 5) presented by Category or Subcategory/PT.
- Overall summaries of any drug-related select AEs by worst CTC grade (any grade, grade 3-4, grade 5) presented by Category or Subcategory/PT.
- Overall summaries of any serious select AEs by worst CTC grade (any grade, grade 3-4, grade 5) presented by Category or Subcategory /PT.
- Overall summaries of drug-related serious select AEs by worst CTC grade (any grade, grade 3-4, grade 5) presented by Category or Subcategory /PT.
- Overall summaries of any select AEs leading to discontinuation by worst CTC grade (any grade, grade 3-4, grade 5) presented by Category or Subcategory /PT.
- Overall summaries of drug-related select AEs leading to discontinuation by worst CTC grade (any grade, grade 3-4, grade 5) presented by Category or Subcategory /PT.
- Summary of frequency of unique select AEs by Category.

A by-subject select AE listing will be provided.

### **7.6.7     Immune-Mediated Adverse Events (US Submission)**

A by-subject listing of IMAEs will be provided. For new studies which collect investigator assessment of potential IMAE data, a by-subject listing of AEs considered as immune-mediated events per investigator but not qualified for IMAEs definition will also be provided.

### **7.6.9     *Multiple Events***

A listing displaying the unique instances of all AEs, i.e., after duplicates have been eliminated and overlapping and contiguous occurrences of the same event (i.e. same PT) have been collapsed will be provided.

### **7.6.10    *Laboratory Parameters***

The analysis population for each laboratory test is restricted to treated subjects who underwent that laboratory test. Laboratory tests (in addition to the tests specified below) with CTC criteria collected in the specific studies may also be included in the summaries.

#### **7.6.10.1   *Hematology***

The following will be summarized as worst CTC grade on-treatment per subject and as shift table of worst on-treatment CTC grade compared to baseline CTC grade per subject: hemoglobin (HB), platelets, white blood counts (WBC), absolute neutrophils count (ANC) and lymphocyte count (LYMPH).

A by-subject listing of these laboratory parameters will be provided.

#### **7.6.10.2   *Serum Chemistry***

The following will be summarized as worst CTC grade on-treatment per subject and as shift table of worst on-treatment CTC grade compared to baseline CTC grade per subject: ALT, AST, alkaline phosphatase (ALP), total bilirubin and creatinine.

A by-subject listing of these laboratory parameters will be provided.

#### **7.6.10.3   *Electrolytes***

The following will be summarized as worst CTC grade on-treatment per subject and as shift table of worst on-treatment CTC grade compared to baseline CTC grade per subject: sodium (high and low), potassium (high and low), calcium (high and low), magnesium (high and low), and Glucose Serum (fasting hyperglycemia and hypoglycemia regardless of fasting status).

A by-subject listing of these laboratory parameters will be provided.

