Chemistry (Excluding LFTs)	X	X	X	X	X	X		X	Predose; includes assessments for sodium, potassium, chloride, total serum calcium, magnesium, phosphorus, BUN, creatinine, c-reactive protein, glucose, total protein, albumin, amylase, lipase, and LDH.
Methemoglobin	X	X	X	X	X			X	Collect predose. Starting with C2D1, collect every cycle and as clinically indicated.. Methemoglobin levels to be assessed on arterial or venous blood sample.
Reticulocyte counts, haptoglobin and LDH	X	X	X	X	X			X	Reflex when methemoglobin is elevated over ULN. Additional samples as clinically indicated.
CBC with Differential and Platelets	X	X	X	X	X	X		X	Predose.

Table 2-3: On-Treatment: BMS-986205 + Nivolumab (Multiple 4-Week Cycles) Procedure Outline (CA017076)

Procedure	Cycle 1 (4 weeks)				Cycle 2-12 (4-week cycles)			End of Treatment ^{a,b,c}	Notes
	D1	D8	D15 (±2 days)	D22 (±2 days)	D1	D15 (±2 days)	D22-28		
LFT Assessments	X	X	X	X	X	X		X	Predose; includes AST, ALT, total bilirubin, direct bilirubin (only if total bilirubin is elevated), alkaline phosphatase, and GGT (only when alkaline phosphatase is increased to ≥ Grade 2).
Thyroid Function Tests					X See notes (every 2 cycles)			X	Collect every 2 cycles, predose, beginning with C3D1 and at the end of treatment. To include TSH with reflex testing to free T3 and free T4 if TSH abnormal. Results should be examined by the investigator or appropriate designee within 48 hours of dose administration.
Pregnancy Test (WOCBP)	X				X			X	Serum or urine pregnancy test must be performed (urine pregnancy test: minimum sensitivity 25 IU/L or equivalent units of hCG) within 24 hours prior to administration of nivolumab. If pregnancy test is positive, hold all study drugs and perform confirmatory testing. If pregnancy is confirmed, permanently discontinue all study drug and immediately notify sponsor per Section 9.2.5 .

Table 2-3: On-Treatment: BMS-986205 + Nivolumab (Multiple 4-Week Cycles) Procedure Outline (CA017076)

Procedure	Cycle 1 (4 weeks)				Cycle 2-12 (4-week cycles)			End of Treatment ^{a,b,c}	Notes
	D1	D8	D15 (±2 days)	D22 (±2 days)	D1	D15 (±2 days)	D22-28		
Adverse Event Reporting and Concomitant Medication Assessments									
Concomitant Medication Assessments	X	X	X	X	X	X	X	X	Review prior to dosing.
Monitor for Nonserious Adverse Events				X					Nonserious AEs will be collected starting with the first dose of study drug and through 100 days post last dose of study drugs.

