^b For subjects who complete all scheduled cycles of therapy, the EOT visit will be the same as the last scheduled and completed on-treatment visit (eg, Cycle 2 Day 22) and the start of the Week 1 Clinical/Safety Follow-Up visit.

^c For subjects who do not complete all scheduled cycles of therapy, the EOT visit will be the most recent on-treatment visit (with all available safety and response data) and does not need to be repeated, and will be considered the start of the Week 1 Clinical/Safety Follow-Up visit.

Table 2-4: Follow-Up Procedure Outline (CA017076)

Procedure	Clinical Safety Follow-Up ^a			Notes
	FU 1 30 days (± 10 days)	FU 2 60 days (± 10 days)	FU 3 100 days (± 10 days)	
Safety Assessments				
Symptom-Directed Physical Examination	X	X	X	
Vital Signs	X	X	X	Includes body temperature, seated blood pressure, and heart rate. Blood pressure and heart rate should be measured after the participant has been seated quietly for at least 5 minutes.
Laboratory Tests				
Chemistry (Excluding LFTs)	X	X	X	Includes assessments for sodium, potassium, chloride, total serum calcium, magnesium, bicarbonate/carbon dioxide, phosphorus, BUN, creatinine, glucose, total protein, albumin, amylase, lipase, and LDH.
Methemoglobin	X	X	X	Only to be drawn if above ULN at last assessment; not required during follow up.
Reticulocyte count, LDH, and haptoglobin	X	X	X	Reflex when methemoglobin is elevated over ULN. Additional samples as clinically indicated.
CBC with Differential and Platelets	X	X	X	Additional samples as clinically indicated.
LFT Assessment	X	X	X	For participants with LFT abnormalities following the last dose of study drug, consider collecting weekly until normalized. Includes AST, ALT, total bilirubin, direct bilirubin (only if total bilirubin is elevated), alkaline phosphatase, and GGT (only when alkaline phosphatase is increased to ≥ Grade 2).

Table 2-4: Follow-Up Procedure Outline (CA017076)

[figure not shown]
Procedure	Clinical Safety Follow-Up ^a			Notes
	FU 1 30 days (± 10 days)	FU 2 60 days (± 10 days)	FU 3 100 days (± 10 days)	
Thyroid Function Tests	X	X	X	To include TSH with reflex testing (free T3 and free T4).
Pregnancy Test	X	X	X	For WOCBP; serum or urine pregnancy test may be performed (clinic urine pregnancy test: minimum sensitivity 25 IU/L or equivalent units of hCG). If positive, perform confirmatory testing. If pregnancy is confirmed, immediately notify sponsor per Section 9.2.5 .

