7.1.1 BMS-986205 Administration

A bottle of BMS-986205 should be dispensed to participants at Day 1 of each cycle.

BMS-986205 is administered as a tablet. The tablet must be administered by mouth, swallowed whole, and not be crushed, chewed, dissolved, or altered in any way. BMS-986205 100 mg oral daily dose must be administered with a meal at approximately the same time each day. On the morning of Cycle 0 Days 1 and 14, and Cycle 1 Day 1 when serial PK samples are collected, after fasting for at least 10 hours, each participant will receive a single oral dose of BMS-986205 within approximately 5 minutes of completing a meal. At the time of dosing, approximately 240 mL of water will be administered to the participant along with BMS-986205. The time of BMS-986205 administration will be called “0” hour.

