7.5 Preparation/Handling/Storage/Accountability

The IP should be stored in a secure area according to local regulations. It is the responsibility of the investigator to ensure that IP is only dispensed to study participants. The IP must be dispensed only from official study sites by authorized personnel according to local regulations.

The product storage manager should ensure that the study treatment is stored in accordance with the environmental conditions (temperature, light, and humidity) as determined by BMS. If concerns regarding the quality or appearance of the study treatment arise, the study treatment should not be dispensed and BMS should be contacted immediately.

Study treatment not supplied by BMS will be stored in accordance with the package insert.

Documentation for IP (whether supplied by BMS or not) must be maintained that includes all processes required to ensure drug is accurately administered. This includes documentation of drug storage, administration and, as applicable, storage temperatures, reconstitution, and use of required processes (eg, required diluents, administration sets).

Refer to the current IBs for BMS-986205 and nivolumab for complete storage, handling, and dispensing information.

7.5.1 *Retained Samples for Bioavailability/Bioequivalence*

Not applicable.

7.6 *Treatment Compliance*

At scheduled PK sample collection as well as laboratory evaluation days, BMS-986205 and associated meal will be administered to the participant in the clinical facility. At all other times throughout the study, BMS-986205 will be administered on an out-participant basis, except when participants are seen in the clinical facility for administration of nivolumab, assessment of AEs, and laboratory evaluation. Trained medical personnel will dispense BMS-986205 to the participants. Treatment compliance will be monitored by drug accountability, as well as by recording BMS-986205 administration in the participant pill diary, medical record, and CRF. Participants should bring all drug containers for BMS-986205 to each study visit for drug reconciliation.

7.6.1 *Treatment of Drug-Related Infusion Reactions*

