9.4.1 Clinical Safety Laboratory Assessments

Investigators must document their review of each laboratory safety report.

A central/local laboratory will perform the analyses and will provide reference ranges for these tests.

Results of clinical laboratory tests performed on Day -1 must be available prior to dosing. [Table 9.4.1-1](#) lists the clinical laboratory tests that will be performed.

Table 9.4.1-1: Clinical Laboratory Assessments

Hematology	
Hemoglobin	
Hematocrit	
Total leukocyte count, including differential	
Platelet count	
Methemoglobin	
Reticulocyte counts and haptoglobin (at baseline and reflex when methemoglobin is elevated over ULN)	
PT/aPTT/INR	
G6PD, quantitative or qualitative - screening only	
Serum Chemistry	
Aspartate aminotransferase (AST)	Total protein
Alanine aminotransferase (ALT)	Albumin
Total bilirubin	Sodium
Direct bilirubin (only if total bilirubin is elevated)	Potassium
Alkaline phosphatase	Chloride
GGT only when alkaline phosphatase is abnormal	Total serum calcium
Lactate dehydrogenase (LDH)	Phosphorus
Creatinine	Magnesium
Blood urea nitrogen (BUN)	Bicarbonate/carbon dioxide
Amylase	Uric acid - screening only
Lipase	Glucose - Fasting at screening only
C-reactive protein	Creatinine clearance (CrCl) - screening only
	Ferritin - screening only
Urinalysis (at screening)	
Protein	
Glucose	
Blood	
Leukocyte esterase	
Specific gravity	
pH	
Microscopic examination of sediment will be done if blood, protein, or leukocyte esterase is positive on dipstick.	
Other	
24 hour urine collection for testing of p-chloroaniline	
Serology	
Serum for hepatitis C antibody (if Hepatitis C antibody is positive reflex to hepatitis C RNA), hepatitis B surface antigen, HIV-1, HIV-2 antibody.	

Table 9.4.1-1: Clinical Laboratory Assessments

Other Analyses
Pregnancy test (WOCBP only)
TSH with free T3 and free T4 at screening and TSH with reflex to free T3 and free T4 as applicable on treatment phase
FSH (if needed to document postmenopausal status as defined in Appendix 4)

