  - On-treatment evaluations (laboratory tests, pulse oximetry and vital signs) will be defined as evaluations taken after the day (and time, if collected and not missing) of first dose of study treatment. For subjects who are off study treatment, evaluations should be within a safety window of 100 days after the last dose of study treatment if a participant received BMS-986205 + NIVO (or 30 days after the last dose of study treatment if a participant received only BMS-986205).

- Post baseline period by phase:
  - Mono lead-in period starts with the first dose of BMS986205 and end prior to first dose of nivolumab.
    - ◆ Mono lead-in AEs will be defined as AEs with an onset date and time on or after the date and time of the first dose of initial mono study treatment (or with an onset date on or after the day of first dose of initial mono study treatment if time is not collected or is missing) and prior to the date-time of the first dose of nivolumab (or with an onset date prior to the day of first dose of nivolumab if time is not collected or is missing). For subjects who discontinue during Mono lead in, AEs will be included if event occurred within a safety window of 30 days after the last dose of BMS-986205 initial mono study treatment. No “subtracting rule” will be applied when an AE occurs both pre-treatment and post-treatment with the same preferred term and grade.
    - ◆ Mono lead-in evaluations (laboratory tests, pulse oximetry and vital signs) will be defined as evaluations taken after the day and time of the first dose of initial mono study treatment (or with a start date after the day of first dose of initial mono study treatment if time is not collected or is missing) and prior to the date-time of the first dose of nivolumab (or with a start date on or prior to the day of first dose of nivolumab if time is not collected or is missing). For subjects who discontinue during Mono lead in, evaluations will be included if evaluation is taken within a safety window of 30 days after the last dose of BMS-986205 initial mono study treatment.
  - Combination Treatment Period starts with the first dose date-time of initial nivolumab.

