### **7.6 *Safety***

Analyses in this section will be tabulated for all treated subjects by phase (monotherapy lead-in, combination) and overall, unless otherwise specified.

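### SAP 7.6.10.3 grades high glucose only as fasting hyperglycemia, but no glucose draw in the combination phase has to be fasting

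*SAP*

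**What the plan says.** SAP 7.6.10.3 summarises worst on-treatment CTC grade, and its shift from baseline, for several analytes including "Glucose Serum (fasting hyperglycemia and hypoglycemia regardless of fasting status". SAP 7.6 has the safety results "tabulated for all treated subjects by phase (monotherapy lead-in, combination) and overall".

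On collection, Protocol Table 9.4.1-1 states "Glucose - Fasting at screening only". The screening schedule (Table 2-1) names fasting glucose. The later schedules list glucose without that condition:

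- Combination cycles (Table 2-3): "magnesium, phosphorus, BUN, creatinine, c-reactive protein, glucose, total protein, albumin, amylase, lipase, and LDH". The lead-in list in Table 2-2 treats glucose the same way.
- Follow-up (Table 2-4): "phosphorus, BUN, creatinine, glucose, total protein, albumin, amylase, lipase, and LDH".

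Protocol 7.1.1 adds a fast of at least 10 hours tied to dosing on three days: "On the morning of Cycle 0 Days 1 and 14, and Cycle 1 Day 1 when serial PK samples are collected, after fasting". Protocol 7.6 says that on PK sampling days "as well as laboratory evaluation days, BMS-986205 and associated meal will be administered to the participant in the clinical facility".

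SAP 6.1 places a laboratory value in the lead-in if it precedes the first nivolumab dose, "or with a start date on or prior to the day of first dose of nivolumab if time is not collected or is missing". Combination-phase values are those taken after that dose.

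**The concern.** The analysis plan asks for a fasting measurement that the protocol does not arrange to collect once nivolumab has started. Two readings of the SAP are open to the programmer, and neither is satisfactory. If only samples known to be fasting are used, high glucose after nivolumab may drop out of the grade and shift tables, or the row may rest on a small, unplanned subset. If every glucose value is used, values of unknown status are reported under a fasting label.

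Laboratory abnormalities are part of the primary endpoint (Table 4-1 in both documents). SAP 7.1.1.3 counts diabetes mellitus among the immune-mediated events of special clinical interest, so high glucose under nivolumab is something a reader will look for. SAP 7.6.10 sets each test's denominator as the treated participants who underwent it, without saying whether that means any glucose or fasting glucose. An empty or sparse row could therefore be read as an absence of hyperglycemia.

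**Working it through.** The plan states no figure to reproduce. The check is a count of scheduled glucose draws, from Protocol Tables 2-2, 2-3 and 2-4, assigned to phases by SAP 6.1, with a note of which fall on a morning with a required fast.

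**Where fasts are required after screening.** Only C0D1, C0D14 and C1D1 (Protocol 7.1.1). C0D1 predose is a baseline value. C1D1 chemistry is drawn before nivolumab, and Table 2-3 allows it up to 3 days earlier. SAP 6.1 puts it in the lead-in whether or not its time is recorded. That leaves at most two fast-morning draws after the first dose, C0D14 and C1D1, both in the lead-in.

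**Why it is at most two.** Protocol 7.1.1 attaches the fast to the dose and its meal, not to the chemistry sample. The dose follows within about 5 minutes of completing the meal, so a predose sample could come after eating.

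**Scheduled glucose draws after first dose**

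| Source | 12 cycles | Stop after Cycle 2 | Stop after Cycle 1 | On a required-fast morning |
|---|---|---|---|---|
| Lead-in: C0D8, C0D14, C1D1 predose | 3 | 3 | 3 | at most 2 |
| Cycle 1: D8, D15, D22 | 3 | 3 | 3 | 0 |
| Cycle 2 onward: D1, D15 | 11 × 2 = 22 | 1 × 2 = 2 | 0 | 0 |
| End of treatment | 1 | 1 | 1 | 0 |
| Follow-up visits 1 to 3 | 3 | 3 | 3 | 0 |
| **Combination plus follow-up** | **29** | **9** | **7** | **0** |

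Two draws in the last line may not add to the count. The end-of-treatment visit can coincide with the last chemistry visit (Table 2-3 footnotes). Follow-up visit 3, at 100 ± 10 days, can fall outside the 100-day window. Removing both:

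- 12 cycles: 29 − 2 = 27
- Stop after Cycle 2: 9 − 2 = 7
- Stop after Cycle 1: 7 − 2 = 5

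The number with a required fast is 0 in every case.

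**Share over both phases, using the larger counts**

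- 12 cycles: 2 / (3 + 29) = 2/32 = 6.3%
- Stop after Cycle 2: 2 / (3 + 9) = 2/12 = 16.7%
- Stop after Cycle 1: 2 / (3 + 7) = 2/10 = 20.0%

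These are upper bounds on the share of draws taken on a required-fast morning. They do not count samples known to be non-fasting.

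**Per participant.** The SAP counts each participant once, at the worst grade. With no guaranteed fasting draw in the combination phase, the number of participants guaranteed to contribute to that row is also 0. The overall column can be filled from C0D14 and C1D1, but both precede nivolumab, so it does not fill the gap.

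**Shift from baseline.** SAP 6.1 takes the latest non-missing value before first dose. That may be the fasting screening sample or one from the C0D1 fast morning, and it would then be compared with later values of unknown fasting status.

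**The case against.** The strongest reply is that this is one direction of one analyte in a descriptive table, in a study sized at 12 PK-evaluable participants with no hypothesis test. Every value is listed (SAP 7.6.10.3), so at this size a reader can inspect them all. Protocol 9.2.7 sends abnormalities to the adverse event record if they are clinically significant, need corrective therapy, or interrupt or stop treatment. Diabetes mellitus is also listed as an immune-mediated event (SAP 7.1.1.3 and 7.6.7). All of this stands. It limits the loss to the laboratory summary but does not repair the row.

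Second, draws are predose, and on laboratory days the dose and meal are given on site, so many samples may in fact be fasting. Status may be recorded on the CRF or handled in the Data Presentation Plan, neither of which is in the documents. That is possible, so the finding is the absence of a guarantee and of a stated rule, not proof that samples were non-fasting. SAP 7.6.10 permits extra CTC-graded summaries but does not commit to one for non-fasting glucose.

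Third, shares of draws are not the unit the table reports. This is fair. The per-participant statement matters more, and in the combination phase it gives the same zero.

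Fourth, a three-way split in so few participants will have sparse cells, and if status was never collected everything falls under unknown. That is true, but such a table would at least show what the data can support.

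**Conclusion.** The concern holds. As written, the combination-phase grade and shift rows for high glucose have no input guaranteed by the protocol: 0 of 27 to 29 scheduled draws for a 12-cycle completer, 0 of 7 to 9 for a participant stopping after Cycle 2, and 0 of 5 to 7 after Cycle 1. The hypoglycemia rows are unaffected, and the lead-in row may be supported by up to two fast-morning draws.

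The conclusion rests on reading the SAP's waiver of fasting status as applying to low glucose only. If it was meant for both directions, the word fasting before hyperglycemia contradicts it and the text still needs correcting. It also assumes that no fasting rule for later visits exists outside the two documents. The change should be made because the affected table reports part of the primary endpoint, but the consequence is confined to that table.

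**What to change.** Amend SAP 7.6.10.3 as follows.

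1. Add a worst-value summary and shift for high glucose using all on-treatment values regardless of fasting status, matching the treatment of low glucose. Label it so, and split it by fasting, non-fasting and unknown, with unknown used where status was not collected.
2. Keep fasting hyperglycemia as a separate row restricted to samples recorded as fasting, and show its own denominator.
3. State the criterion for the all-values row. The CTC criteria are not in the documents. If the glucose grade applies only to fasting samples, report the highest value and counts above the laboratory's upper limit of normal in place of a grade.
4. Keep the SAP 6.1 baseline, including the C0D1 predose value, and flag shifts where fasting status differs between baseline and the later value or is unknown.

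The cost is SAP wording plus modest programming: the additional row and footnote, repeated by phase and overall and in the two unit systems of SAP 7.1.2. No new samples or visits are needed. Some mild post-meal elevations will be counted in the all-values row. The split and flag make them visible where status was recorded.
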